2.2.2 Treatments and Assignment to Treatments

Approximately 120 patients will be randomized to 2:1 to 150 mg QD of DCC-2618 versus placebo. Randomization will be stratified by:

- Patients who have received 3 prior anticancer treatments versus patients who have received ≥ 4 prior anticancer treatments.
- ECOG performance status=0 versus ECOG performance status=1 or 2.

Patients will continue on the current treatment until the time of disease progression by modified RECIST from the independent radiological review, unacceptable toxicity, or withdraw of consent. Upon progression confirmation by independent radiological review, study treatment will be unblinded.

At that time:

Patients randomized to DCC-2618 150 mg QD will be given the option to:

- continue DCC-2618 at an increased dose of 150 mg BID, or
- continue treatment on study with the same dose if the Investigator feels the patient is receiving benefit from DCC-2618 or if dose escalation may not be tolerable for the patient (dose escalation is not permitted at a later time during the study), or
- discontinue DCC-2618.

Patients randomized to placebo will be given the option to:

- cross over to receive DCC-2618 150 mg QD, or
- discontinue the study

Patients randomized to placebo who cross over to receive DCC-2618 150 mg QD and have disease progression by modified RECIST based on Investigator assessment will be given the option to:

- continue DCC-2618 at an increased dose of 150 mg BID
- continue treatment on study with the same DCC-2618 dose if the Investigator feels the patient is receiving benefit from DCC-2618 or if dose escalation may not be tolerable for the patient (dose escalation is not permitted at a later time during the study) or
- discontinue DCC-2618.

2.3 Determination of Sample Size

The sample size selection of approximate 120 patients (n=80 DCC-2618, n=40 placebo) was based on considerations for powering of the primary endpoint, key secondary endpoint, detection of rare safety events and overall exposure to DCC-2618, and assuming 15% patient dropout. Patients will be randomized in a 2:1 ratio of DCC-2618 versus placebo.

This sample size [105 patients (n=70 DCC-2618, n=35 placebo) with 90 events (55 DCC-2618, 35 placebo) at the final analysis] will have at least 90% power to detect a difference in PFS between DCC-2618 and placebo assuming a median PFS of 4.5 months for DCC-2618 and 1 month for placebo. Moreover, this assumes 9 months of uniform recruitment and 6 additional months of follow-up (total patient follow-up of 15 months).

Furthermore, 105 patients (n=70 DCC-2618, n=35 placebo) will have approximately 80% power to detect a 0.2 difference in ORR assuming that the ORR for DCC-2618 = 0.22 and the ORR for placebo = 0.02.

In addition, a minimum sample size of 80 DCC-2618 patients allows adequate power to detect the incidence of rare safety events. A sample of 80 patients yields 95% probability that the study will reveal at least one occurrence of all safety events that occur in patients at a rate of 4.0% or greater. This in combination with the exposure to DCC-2618 from other studies conducted in this clinical program will meet the recommendations for overall exposure recommended by FDA.

Where required, safety personnel at the Sponsor or designee may be unblinded to a patient's study drug assignment to meet reporting requirements to regulatory agencies. In addition, the Investigator, patient, Sponsor, and study team will be unblinded at the time the patient has disease progression by modified RECIST based on independent radiology review.

At no point in time before official full study unblinding will any efficacy and safety analyses be conducted by the Sponsor or Sponsor representatives, unless there is explicit permission to do so, for instance high level efficacy assessment for the purposes of an Independent Data Monitoring Committee (IDMC) review to determine the adequacy of the risk/benefit profile of the drug as it pertains to the conduct of the clinical trial.

3 GENERAL ANALYSIS CONVENTIONS

Statistical analysis will be performed using SAS[®] (version 9.4 or newer).

3.1 Statistical Analysis Periods

Based on the study design, two main analysis periods will be defined as follows:

- Double-blind treatment analysis period
 - from the randomization date to the last follow-up date
 - if a patient did not have disease progression based on independent radiologic review or
 - if a placebo patient did not cross over to DCC-2618 treatment or
 - if a patient was initially treated with DCC-2618 and did not continue to receive DCC-2618 at 150mg QD or escalate to 150mg BID after disease progression based on independent radiologic review from the randomization date to the first disease progression date if a patient was initially treated with DCC-2618 and continued to receive DCC-2618 at 150mg QD after disease progression based on independent radiologic review
 - from the randomization date to the day immediately before the first dose of DCC-2618 150mg BID if a patient escalated to DCC-2618 150mg BID after disease progression based on independent radiologic review
 - from the randomization date to the day immediately before the first dose of DCC-2618 150mg QD if a patient crossed over from placebo to receive DCC-2618 at 150mg QD after disease progression based on independent radiologic review
- Open-label analysis period
 - from the day immediately after the first disease progression based on independent radiologic review to the last follow-up date if a patient was initially treated with DCC-2618 and continued to receive DCC-2618 150mg QD after disease progression based on independent radiologic review
 - from the first dose date of DCC-2618 150mg BID to the last follow-up date if a patient was initially treated with DCC-2618 and escalated to DCC-2618 150mg BID after disease progression
 - from the first dose date of DCC-2618 150mg QD to the last follow-up date if a patient crossed over from placebo to receive DCC-2618 150mg QD after disease progression based on independent radiologic review

The primary efficacy endpoint, progression-free survival, will be defined and analyzed only during the double-blind treatment analysis period.

Overall survival will be defined and analyzed throughout patients' entire on study period. The data cut-off for the primary analysis will occur when 90 PFS events have occurred. It is expected that the primary analysis will occur approximately 6 months after the last patient is enrolled into the trial.

As of the primary efficacy analysis, the evaluation of the efficacy and safety of DCC-2618 against the placebo will be mainly based on the data collected during the double-blind treatment analysis period. The analysis during this period will be detailed in [Sections 3.2 to 10.10](#).

For data collected during the open-label analysis period and entered in the database by the data cut-off date or at the final database lock, statistical analysis will be described in [Section 11](#).

3.2 Visit Windows

The protocol visit windows are defined the same for blinded treatment and open label treatment phases. Visits will be analyzed per the electronic case report form (eCRF) collection. Unscheduled visits will be mapped to a scheduled visits if possible, using a window based on all the available actual visit dates for the scheduled visits.

Reference start date will be defined as Cycle 1 Day 1 visit date. Study Day will be calculated from the reference start date and used to show start/stop day of the assessments and events as follows,

- For assessments/events on/after the reference start date:
$$\text{Study Day} = (\text{date of assessment/event} - \text{reference start date}) + 1$$
- For assessments/events before the reference start date:
$$\text{Study Day} = (\text{date of assessment/event} - \text{reference start date})$$

3.3 Baseline

Unless specified otherwise, baseline measurements will be the most recent (ie, last non-missing) value collected from screening until prior to receiving the first dose of study medication (Cycle 1 Day 1).

3.4 Handling of Repeated and Unscheduled Assessments

In general, for by-visit summaries, data recorded at nominal visits will be presented.

Laboratories, vital signs, ECG, and ECHO/MUGA results at unscheduled visits and repeated assessments will not be included in the by-visit summaries however will contribute to the best/worst case value, and last on-treatment visit, where applicable.

Tumor assessments at unscheduled visits will be used for the derivation of the primary endpoint and other efficacy endpoints.

3.5 Coding Dictionaries

Medical history and adverse events (AE) will be coded using Medical Dictionary for Regulatory Activities (MedDRA), Version 21.1 or higher. Prior and concomitant medications and procedures will be coded using the World Health Organization (WHO) Drug Dictionary (SEP 2018) or higher.

3.6 General Analysis Conventions

Continuous variables will be summarized using descriptive statistics (number of patients, mean, median, standard deviation, minimum, and maximum). Categorical variables will be summarized using frequencies and proportions. Time-to-event data will be summarized via Kaplan-Meier (KM) methodology using the 25th, 50th (median), and 75th percentiles with associated 2-sided 95% confidence intervals.

4 ANALYSIS POPULATIONS

4.1 Intention-to-treat Population

The Intention-to-treat Population (ITT) population is defined as all patients who signed the informed consent and were randomized.

The ITT population will be used for all efficacy analysis as a primary analysis set with treatment assignment based on randomization.

4.2 Safety Population

The Safety population is defined as all patients who have received at least 1 dose of study drug.

The safety population will be used for all safety analyses with treatment actually received.

4.3 Per Protocol Population

The Per Protocol (PP) population is defined as randomized patients who do not have important protocol deviations that are expected to compromise the efficacy and/or safety assessments as follows,

- Inclusion/exclusion criteria deviations
- Patient receiving wrong treatment
- Patient receiving incorrect dose
- Patient receiving prohibited medications

The criteria for such important protocol deviations will be determined by the sponsor and documented in a separate file. At the primary efficacy analysis, protocol deviations resulting in exclusion from the PP population will be identified by the sponsor and documented prior to the database lock.

4.4 PK Population

The PK population will include all randomized subjects who received at least 1 dose of DCC-2618 and had at least 1 non-missing PK concentration in plasma reported for DCC-2618 or DP-5439.

The PK population will be used for all PK analyses.

5 PATIENT DISPOSITION

Patient disposition will be summarized overall for all patients who enrolled in the study (ie, signed the informed consent for the study and were randomized). In addition, the number of patients in each population (ie, ITT, safety, PK, and PP) will be displayed. The number and proportion of patients among the safety population who have discontinued from treatment and the study will be summarized along with the reason for discontinuation.

6 PROTOCOL DEVIATIONS

A protocol deviation is any change, divergence, or departure from the study design or procedures defined in the clinical protocol. Protocol deviations will be classified by medical review prior to primary analysis and major protocol deviations will be identified.

The Sponsor or designee will be responsible for producing the final protocol deviation file (formatted as a Microsoft Excel file). This file will include a description of each protocol deviation and whether or not this deviation is classified as a major protocol deviation. This file will be finalized prior to database lock and study unblinding.

In addition, the sponsor will determine the important protocol deviations that may significantly impact the completeness, accuracy, and/or reliability of the trial data; that may significantly affect a subject's rights, safety, or well-being (ICH E3 R1 Guidelines 2013). Patients who have important deviations will be excluded from the Per-protocol population. All the important deviations will be summarized and described in the clinical study report.

7 DEMOGRAPHICS AND BASELINE CHARACTERISTICS

7.1 Demographic Characteristics

Demographic and baseline characteristics at study entry will be summarized for the safety and intention-to-treat populations.

Demographic and baseline variables to be summarized are:

- Continuous variables
 - Age (years) at time of consent
 - Height (cm)
 - Weight (kg)
- Categorical variables
 - Gender
 - Race
 - Ethnicity
 - Screening ECOG (stratification variable)
 - Number of prior therapies (stratification variable)

7.2 Medical History

The number and percentage of patients with each medical history condition will be summarized for the safety population by system organ class and preferred term as coded using MedDRA Version 21.1 or higher.

7.3 Cancer History and Prior Cancer Therapy

Histologic diagnosis of GIST, tumor mutation status, histology, stage at initial diagnosis, and time since the initial diagnosis in years (calculated from the informed consent date) will be summarized for the Safety Population. For prior cancer therapy, the number of patients and the type of systemic therapy, surgery, and radiation will be summarized along with the number of systemic therapy regimens per patient for the safety population.

8 EFFICACY ANALYSIS

8.1 Primary Efficacy Analysis

The primary endpoint of PFS (reported in weeks) is defined as the interval between the date of randomization and the earliest documented evidence of the first disease progression based on the independent radiologic review or death due to any cause on initially assigned study treatment, whichever comes earlier. In the following situations, PFS will be re-defined otherwise or censored:

- For patients who do not have evaluable radiologic assessment (including those randomized but untreated due to death or any other cause), PFS will be censored at randomization date (PFS=1 day) unless they die within 2 cycles of treatment (8 weeks plus 3 days allowing for a late radiologic assessment within the visit window). If patients die within 2 cycles of treatment (8 weeks plus 3 days), they are considered to have a PFS event at death date
- For patients who only have non-measurable lesion according to modified RECIST Version 1.1 (non-nodal lesions must be ≥ 1.0 cm in the long axis or \geq double the slide thickness in the long axis) within 21 days prior to the first dose of study treatment, PFS will be censored at the date of latest evaluable progression-free radiologic assessment or patients will be considered to have disease progression at the date of new lesion(s) or unequivocal progression in non-target disease
- For patients who undergo surgical resection of target or non-target lesions, who have received other anticancer treatments than the study treatment before documented date of the first disease progression, PFS will be censored at the date of the latest evaluable progression-free radiologic assessment
- For patients who have not progressed and have not died, PFS will be censored at the time of the latest date of evaluable progression-free radiologic assessment if at most one missed/non-evaluable assessment prior to this assessment
- For patients who have first disease progression or die after two or more consecutive missed/non-evaluable assessments, the patient will be censored at the time of the evaluable radiologic assessment immediately prior to the two or more consecutive missed/non-evaluable radiologic assessments. The missed/non-evaluable assessments include both the scheduled assessments when a patient was on treatment and the hypothetical assessments (the expected assessments as if the patient was still on

treatment) after a patient discontinued treatment or withdrew for reasons other than progressed disease. For patients who have first disease progression documented between scheduled assessments, progression date is defined as the date of new lesion (if progression is due to new lesions) or defined as the earliest of the scan dates of the components that triggered the progression per independent radiologic review (if progression is due to increase in sum of measured lesions).

Analysis for PFS will be stratified by the randomization stratification factors [prior lines of therapy (3 versus ≥ 4) and ECOG (0 versus 1 or 2)]. The p-value will be from a 2-sided stratified Log-rank test at 0.05 significant level for evaluation of treatment difference. Point estimate of hazard ratio will be obtained from a Cox regression model with treatment and the randomization stratification factors as fixed factors and its 95% CI will be obtained using Wald method. PFS time will be summarized via KM methodology using the 25th, 50th (median), and 75th percentiles and pre-specified timepoints, each with associated 2-sided 95% confidence intervals.

Analyses will be performed using the ITT population as the primary efficacy analysis and PP population as supportive.

Sensitivity analyses maybe performed if deemed necessary.

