9.8.5. Efficacy Analysis

9.8.5.1. Primary Endpoint: Progression-free Survival Analysis

The primary endpoint of PFS (reported in weeks) is defined as the interval between the date of randomization and the earliest documented evidence of disease progression based on the independent radiologic review, or death due to any cause. Patients who undergo surgical resection of target or non-target lesions, who have received other anticancer treatments, or patients who do not have a documented date of progression or death due to any cause will be censored at the date of the last assessment. Analysis for PFS will be stratified by the randomization stratification factors [prior lines of therapy (3 versus ≥ 4) and ECOG (0 versus 1 or 2)]. The p-value will be from a 2-sided stratified Log-rank test at 0.05 significant level for evaluation of treatment difference. Point estimate of hazard ratio will be obtained from a

Cox regression model with the treatment and the randomization stratification factors as fixed factors and its 95% CI will be obtained using the Wald method.

Analysis will be using the ITT population as the primary analysis and PP as supportive. Progression-free survival will have sensitivity analyses performed which will be further detailed in the SAP.

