8.3.4 PFS Based on Investigator Assessment

As a sensitivity analysis to the primary efficacy analysis, PFS (reported in weeks) is defined as the interval between the date of randomization and the earliest documented evidence of disease progression based on Investigator assessment or death on initial study treatment due

to any cause. In the situations mentioned in [Section 8.1](#), PFS based on investigator assessment will be defined or censored in a manner analogous to which is used for PFS based on independent radiologic review.

PFS based on investigator assessment will be analyzed in similar fashion to PFS based on independent radiologic review.

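### SAP 8.1 and 8.3.4 tie the PFS death event to being on initial treatment, which the protocol does not do and the SAP's own rules contradict; read literally, some deaths get neither an event nor a censoring date

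*SAP*

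**What the plan says.** Protocol 9.8.5.1 ends PFS at "the earliest documented evidence of disease progression based on the independent radiologic review, or death due to any cause". Protocol 9.8.5.3.4 defines Investigator PFS in the same way. Neither section requires the patient to be on treatment at death.

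SAP 8.1 adds a condition: "death due to any cause on initially assigned study treatment, whichever comes earlier". SAP 8.3.4 does the same for Investigator PFS ("based on Investigator assessment or death on initial study treatment due" to any cause), and there the condition plainly attaches to death. SAP section 1 says that the SAP sets out its differences from the protocol's methods, but this difference is not identified or explained.

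SAP 8.1 then lists situations in which PFS is redefined or censored. Three of them concern death:

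- The rule for patients with no evaluable scan, "including those randomized but untreated due to death or any other cause", says: "If patients die within 2 cycles of treatment (8 weeks plus 3 days), they are considered to have a PFS event at death date".
- Ordinary censoring at the last scan is confined to patients who have neither progressed nor died.
- The missed-scan rule says: "For patients who have first disease progression or die after two or more consecutive missed/non-evaluable assessments, the patient will be censored" at the last evaluable scan before the gap. Missed assessments include hypothetical ones "after a patient discontinued treatment or withdrew for reasons other than progressed disease".

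SAP 3.1 restricts PFS to the double-blind analysis period. For a patient without progression on independent review, that period runs from randomization to last follow-up, not to last dose.

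**The concern.** The event definition of the primary endpoint should give every randomized patient exactly one outcome. Here the headline sentence and the rules beneath it can give different answers for a patient who dies after stopping drug. Two competent programmers could code that patient differently.

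Such patients are foreseeable. The protocol provides for stopping drug because of unresolved toxicity (5.3.2), after emergency unblinding (5.11), and on clinical deterioration without progression confirmed by independent review (6.10.1). After the end-of-treatment scan, Table 1 schedules only telephone contact. Survival follow-up continues (6.10.2, 8.1), so the deaths will be known, and for these patients death is usually the only PFS event still possible. Because 90 PFS events trigger the data cut-off (SAP 3.1), the coding choice also affects when the trial reads out.

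**Working it through.** **1. The patient who falls between the rules.** Take a patient with measurable disease and at least one evaluable scan, no progression on independent review, no resection and no other anticancer treatment. The patient stops drug and dies before two consecutive assessments are missed. Applying SAP 8.1 in turn:

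- No-evaluable-scan rule: does not apply, because the patient has an evaluable scan.
- Non-measurable-disease rule and resection/other-treatment rule: do not apply, by construction.
- Ordinary censoring: does not apply, because the patient has died.
- Missed-scan rule: does not apply, because fewer than two assessments were missed.
- Headline sentence: read literally, no event, because the patient was off treatment at death.

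The result is no event and no censoring date. The literal reading has some support in SAP 10.1, which measures the duration of initial assigned treatment from first to last dose.

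**2. How long the gap stays open.** Table 1 of the protocol schedules scans every 28-day cycle through Cycle 4, then every other cycle. The second missed scan therefore falls 2 × 28 = 56 days after the last evaluable scan early on, and 2 × 56 = 112 days after it once scans are every other cycle.

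**3. What the other rules imply.**

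- The no-evaluable-scan rule counts a death within 8 × 7 + 3 = 59 days, including in patients who never took drug. Such patients cannot die on treatment.
- The missed-scan rule censors a death only after two missed assessments, and counts hypothetical assessments after discontinuation. For deaths it would be needless if every off-treatment death were already a non-event.
- SAP 3.1 keeps the period open to last follow-up.

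All three point to counting the death in step 1 as an event.

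**4. Design figures.** Inputs from SAP 2.3: medians 4.5 and 1 month, 70 and 35 patients, 9 months of uniform accrual plus 6 months of follow-up. Assuming exponential PFS, P(event) = 1 − [exp(−6λ) − exp(−15λ)]/(9λ), with λ = ln 2/median.

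- DCC-2618: λ = 0.1540, P = 0.7853, 70 × 0.7853 = 54.97 events.
- Placebo: λ = 0.6931, P = 0.9975, 35 × 0.9975 = 34.91 events.
- Total 89.9, against the stated 55 + 35 = 90. The plan's figure reproduces.

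Schoenfeld power = Φ(|ln HR| × √(D × 2/9) − 1.96), with HR = 1/4.5 = 0.222 and |ln HR| = 1.504:

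- D = 90: 1.504 × 4.472 − 1.96 = 4.77, power above 0.9999.
- D = 63 (27 events lost, an assumed extreme): 1.504 × 3.742 − 1.96 = 3.67, power 0.9999.

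Only 21 events are needed for 90% power at this hazard ratio. Because the cut-off is fixed at 90 events, the definition changes which deaths are events and when the cut-off falls, not the planned event count.

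**The case against.** The strongest reply is that the intended meaning can be recovered. The SAP says that the listed situations redefine or censor PFS, so the specific rules should govern the headline. Similar phrases about initial treatment in SAP 8.2, 8.3.1 and 8.3.5 appear to separate the randomized phase from crossover or dose escalation, not on-drug from off-drug time. Since every patient in the ITT population needs an outcome, the only reading that gives the step 1 patient one is an event at death. The number affected may also be small: Table 1 schedules a scan at the end-of-treatment visit, and progression called on clinical deterioration requires a scan sent for independent review, so some of these patients will have a progression event before they die.

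Most of this stands, and it defeats a stronger reading. A reader might infer that the SAP counts only on-treatment deaths, so that early off-treatment deaths in general are non-events. The documents do not support that: the no-evaluable-scan rule and the missed-scan rule both treat off-treatment deaths as possible events.

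What the reply does not remove is the sentence itself. The phase-of-study meaning is never stated, SAP 10.1 supports the other meaning, and a primary event definition should not have to be inferred from rules that contradict it.

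**Conclusion.** Wrong as written. The condition on death in SAP 8.1 and 8.3.4 is absent from the protocol and conflicts with SAP 8.1's own rules and with SAP 3.1. It leaves one identifiable group of deaths without a defined outcome if applied literally.

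The size cannot be derived, because the documents give neither an off-treatment death rate nor stopping rates by arm; SAP 2.3 states only 15% dropout overall. The effect on the hazard ratio is probably small. A reader might infer that the phrase drops more deaths in the arm treated longer and so biases the comparison in a known direction. That needs arm-level stopping and death rates which the documents do not contain. Nor is there a power problem under the design assumptions. The point is an unambiguous primary event definition that agrees with the protocol.

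**What to change.** In SAP 8.1 and 8.3.4, replace the phrase with: *death due to any cause, regardless of treatment discontinuation, occurring within the double-blind analysis period defined in Section 3.1 (that is, before crossover or open-label DCC-2618 continuation/escalation, applied to both arms), subject to the censoring rules listed below*.

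The limit should refer to the analysis period and not only to the first crossover dose. A crossover limit would cut off placebo deaths in the Investigator PFS analysis while still counting DCC-2618 deaths after unblinding and dose escalation. For PFS by independent review the limit matters little, because progression on that review precedes crossover.

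The cost is SAP wording in two sections, made before unblinding. No data collection, sample size or event target changes. The censoring of later deaths after two or more missed or hypothetical scans stays as the SAP now specifies.
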